6.3 Treatment assignment

Randomization will be stratified by type of donor kidney received (living or deceased donor kidney) and primary versus retransplant recipient. Randomization will be performed using a random number generator.

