Potential study participants will be approached for consent immediately prior to transplantation by the transplant surgeon or appointed representative if they meet the inclusion criteria above and do not fit the exclusion criteria above. If the transplant candidate agrees to participate he/she will be categorized as a living or deceased donor kidney recipient category and as primary or subsequent kidney transplant recipient. The candidate will then be randomized, in a 2:1 fashion, to either the Zortress or Rapamune study arm. Following transplantation all recipients will receive daily Thymoglobulin doses of 1.25 mg/kg starting on POD #1 for 4 to 5 doses adjusted for white blood count and platelet count. All recipients will be administered steroids as methylprednisolone IV for two doses, then oral prednisone at: 500 mg, 200 mg, 125 mg, 50 mg, and 25 mg and will receive delayed Neoral® on POD #2-3 dosed to achieve serum levels of 800 to 1000 ng/ml by immunoassay until 3 months post-transplant, 600-800 ng/ml 3-6 months post-transplant, 400-600 ng/ml 6-12 months post-transplant, and 400 ng/ml > 12 months post-transplant. Zortress® will be started on POD #0 for Zortress study arm recipients, administered bid and dosed to achieve target levels of 3 to 8 ng/ml by approved testing methods; Rapamune® study arm recipients will receive Rapamune once daily, dosed to achieve target levels of 10 to 18 ng/ml by Architect assay, or 8 to 12 by LC-MS methodology. Neoral and Rapamune/Zortress levels will be monitored twice weekly for the first 3 months, once weekly for months 3-6, every other week months 6-12, and monthly thereafter. This pilot study is estimated to take one year for enrollment and three years from the date of last patient enrollment for completion of last patient visit, then several months for completion of paper work. This will be about 4.5 to 5 years.

Efficacy assessments:

- Incidence of graft loss in the first post-transplant year
- Incidence of patient death in the first post-transplant year
- Incidence of acute rejection at 1 year post-transplant

Other assessments:

- Incidence of non-death censored graft loss at 6 months, 2 and 3 years after transplantation
- Number and grade of acute rejection episodes at 6 months, 1, 2, and 3 years after transplantation
- Tolerability of Zortress at 1 year post-transplant
- Estimated GFR at 6 months, 1, 2, and 3 years after transplantation
- Incidence of CMV, EBV and BK infections 1 year after transplantation

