The patient population will be all adults (18-75 years of age) who receive a living donor or deceased donor renal transplant as a first or subsequent renal transplant procedure only (no extra-renal organ transplant recipients). We will invite any patient who would normally be considered for our current Sirolimus®/ Neoral® protocol with Thymoglobulin® and steroid induction to consent for this pilot study and then undergo randomization post-operatively if the transplant surgeon anticipates normal early graft function. If there were significant concerns for prolonged graft dysfunction, then the patients will not be invited into the pilot study. Invited patients would include anyone currently not on steroids prior to transplantation, and those with no known intolerance to any of the drugs mentioned. Patients must also be willing to perform the expectations of the study protocol reliably.

This will be a single center pilot study performed at The Ohio State University Comprehensive Transplant Center. Our center performs approximately 100 to 110 living donor and 90 to 100 deceased donor renal transplants per year. If we assume that at least 150 patients per year qualify for the study, then a conservative estimate of 75 enrolled patients a year is possible. We would propose to enroll a total of 60 patients over 12 months, and then follow these patients for a complete 3 years. We will randomize 2:1 Zortress to Sirolimus using a random number generator.

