6.2 Treatment arms

Patients will be assigned to one of the following “n” treatment arms in a ratio of 2:1; Zortress or Sirolimus started on POD 0, with Solumedrol 500 mg IV in OR as induction, then 5 doses of Thymoglobulin starting morning of POD 1 at 1.25 mg/dose (rounded to nearest 25 mg) with rapid steroid taper over five doses. Neoral will be introduced as renal function recovers, usually starting on POD 2. We will enroll a total of 60 patients.

- Zortress and Neoral, with Thymoglobulin induction and perioperative steroids
- Rapamycin and Neoral, with Thymoglobulin induction and perioperative steroids

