6.4 Treatment blinding

This is an open-label study and thus there will be no blinding.

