7.2 Information to be collected on screening failures

No information will be collected on patients failing the screening process.

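### The plan stratifies randomisation but does not say how allocation within strata is restricted or concealed, and it gives two different times for randomisation relative to the surgeon's entry judgement

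*Combined protocol and SAP*

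**What the plan says.** **Mechanism.** Section 6.3 (Treatment assignment): "Randomization will be stratified by type of donor kidney received (living or deceased donor kidney) and primary versus retransplant recipient". The next sentence is the whole description of method: "Randomization will be performed using a random number generator". Section 5 (Population) adds only the ratio: "We will randomize 2:1 Zortress to Sirolimus using a random number generator". Section 6.2 fixes the total: "We will enroll a total of 60 patients".

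**Concealment.** No section names a sequence holder or a release step. An interactive voice response system and a randomisation number appear in the abbreviations and glossary, but no procedure uses them. Section 6.5.2 leaves dispensing to standard procedures. Section 6.4: "This is an open-label study and thus there will be no blinding".

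**Entry and timing.** Section 5 and the Population paragraph of the synopsis say that consented patients "undergo randomization post-operatively if the transplant surgeon anticipates normal early graft function". The treatment narrative later in the synopsis runs in a different order: consent immediately before transplantation, classification by donor type and transplant history, and then "The candidate will then be randomized, in a 2:1 fashion, to either the Zortress or Rapamune study arm". Only after that does it turn to care following transplantation. Table 7-1 has no row for randomisation.

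**Records.** Section 7.2: "No information will be collected on patients failing the screening process".

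**Analysis.** The synopsis and sections 10.1.2 and 10.2.1 give chi-squared, t, Wilcoxon and log-rank tests. None is described as stratified or adjusted.

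**The concern.** Stratifying brings the arms closer together on a factor only when allocation inside each stratum is restricted, for example by blocks. Independent 2:1 draws inside four strata are the same process as independent 2:1 draws overall. The investigators chose to control donor type. With about 20 Rapamune patients the plan as written does not secure that control, and the unadjusted tests would not restore it.

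The second issue is selection. The surgeon's expectation of graft function decides who is randomised, treatment is open, there is one centre, and the stated rationale is that patients may fare better on everolimus. If the assignment can be seen or is already made when that expectation is formed, the two arms may differ in expected graft function from the start. Graft survival, rejection and eGFR are all exposed to this. The trial aims at equivalency (section 3.1), expects non-inferiority (section 10.5) and may stop early on a between-arm difference (section 6.5.6), so it relies on a fair comparison even as a pilot.

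**Working it through.** **Inputs.** From the documents: N = 60, ratio 2:1, four strata (donor type by primary/retransplant), and 100–110 living and 90–100 deceased donor transplants a year at the centre (section 5). Assumed: the enrolled donor mix follows the centre's, taken as 30/30 in the exact sum and as 52.5% living (105/200) in the simulations. The retransplant share is not given, so 0%, 10% and 20% were tried.

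**Plan's own figure.** 60 × 2/3 = 40 and 60 × 1/3 = 20. No sample size or power calculation exists to reproduce.

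**Step 1: arm sizes under simple 2:1 draws.** Rapamune count X ~ Binomial(60, 1/3).
- SD = √(60 × 1/3 × 2/3) = 3.65; 95% range 13 to 27.
- P(X = 20) = 10.9%.
- P(X ≤ 15) = 10.7% and P(X ≥ 25) = 11.0%, so P(5 or more off 40:20) = 21.7%.

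**Step 2: donor-type gap under simple draws, 30 living and 30 deceased.** The gap is the living share in Zortress minus that in Rapamune. At 40:20 its SD is roughly √(0.25 × (1/20 + 1/40)) = 0.137. Summing over two independent Binomial(30, 1/3) counts gives P(|gap| ≥ 20 points) = 15.8% and P(|gap| ≥ 15 points) = 29%.

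**Step 3: does naming strata change this?** Simulation, 6,000 runs per scenario; ranges cover retransplant shares of 0–20%.

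| Method | SD of Zortress arm size | SD of donor-type gap | P(gap ≥ 20 points) |
|---|---|---|---|
| Simple, no strata | 3.65–3.70 | 0.139–0.140 | 14.6–15.7% |
| Simple within strata | 3.64–3.70 | 0.135–0.140 | 14.0–15.6% |
| Blocks of 3, 6 or mixed within strata | 0.54–1.05 | 0.020–0.040 | 0.0% |

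The first two rows agree within simulation error. The donor-type result does not depend on the retransplant assumption.

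**Step 4: predictability.** With simple draws the best guess is always Zortress, correct 66.7% of the time, and past assignments add nothing. With a known block of 3 (two Zortress, one Rapamune), the chance of a correct guess is 2/3 at position 1, 1/3 × 1 + 2/3 × 1/2 = 2/3 at position 2, and 1 at position 3. The average is 7/9 = 77.8%. The next assignment is certain for (1/3 + 1)/3 = 44% of patients. For a known block of 6 the figures are 74.4% and 29%. Blocks therefore buy balance at some cost in predictability, which is why their sizes must vary and stay undisclosed.

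**Step 5: timing, side by side.** In section 5 and the synopsis Population paragraph the order is consent, surgery, surgeon's expectation of function, randomisation. In the synopsis treatment narrative it is consent, classification, randomisation, then post-transplant care. On the second order the assignment could be known when the surgeon forms the expectation that the first makes a condition of entry.

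**Step 6: strata against eligibility.** Inclusion criterion 2 (section 5.1) admits primary recipients. Sections 4, 5 and 6.3 admit retransplants. Read literally, criterion 2 empties two of the four strata.

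**The case against.** **Silence is not proof of simple randomisation.** A random number generator can also produce permuted blocks within strata, and 6.3 says allocation will be stratified. This stands: a reader might infer that stratification is established to balance nothing, but the documents support that only conditionally. What remains is that the method cannot be reproduced from the text.

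**Missing blocks do not expose the next assignment.** A reader might link the two, but Step 4 shows the reverse: simple draws are the least predictable. The exposure comes from the missing concealment step and the conflicting timing. Nothing in the documents shows that the surgeon has access to the sequence.

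**A missing log is not a missing record.** Section 7.2 concerns screening failures, and extending it to consented patients who are not randomised is inference. Section 11.2 requires consent to be documented in source records, and section 8.2 starts SAE coverage at consent, so such patients could be traced. What is lacking is a log with reasons.

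**The effect on results may be small.** Half of the 22% is a larger control arm, which helps precision: 1/n₁ + 1/n₂ is 0.069 at 25/35, against 0.075 at 20/40. At 15/45 it is 0.089, a standard error about 9% larger. If rejection differed by 10 points between donor types (assumed), a 20-point gap would shift the estimate by 0.20 × 10 = 2 points. The standard error at 10% rejection is √(0.10 × 0.90 × 0.075) = 8.2 points. This stands too: chance imbalance has not been shown to create or hide a rejection difference, and the study is declared exploratory and unpowered. It does not answer the selection route, which is bias and not noise.

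**Conclusion.** The omission is real: no section states the restriction method, the sequence holder or a concealment step. If the generator makes simple 2:1 draws, stratification has no effect. The chance of being 5 or more off 40:20 is then 22%, and the chance of a donor-type gap of 20 points or more is about 16% with 30 living and 30 deceased donors, against about 0% with blocks within strata. Those figures rest on the simple-draw reading and, for the gap, on the centre's donor mix carrying over to the trial. No figure is claimed for the retransplant stratum, because its size is not given and its eligibility is contradicted.

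The balance part alone would be minor. Concealment and timing carry the weight: a surgeon's judgement decides entry to an open-label trial, no safeguard is stated, and one of the two described sequences lets the assignment precede the judgement. The documents do not show that selection would occur, only that the plan does not guard against it. The change should be made.

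**What to change.** 1. In 6.3, state computer-generated 2:1 permuted blocks of randomly varying size (for example 3 and 6) within each stratum. Block sizes are not disclosed to the transplant team, and the list is held by existing staff outside it, such as the dispensing pharmacy.
2. Require that the eligibility decision be irrevocably recorded before the assignment is released.
3. Reconcile section 5, the synopsis Population paragraph and the synopsis treatment narrative to one time of randomisation, after that decision.
4. Reconcile inclusion criterion 2 with the retransplant stratum.
5. In 7.2, log each consented patient who is not randomised, with the reason.

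**Cost.** One list prepared before enrolment, an existing staff member to hold it, and a short log; no extra patients or procedures. Sparse strata will leave some blocks incomplete. Allocation becomes slightly more predictable than with simple draws, which varying and undisclosed block sizes limit but do not remove.

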6.4 Treatment blinding

This is an open-label study and thus there will be no blinding.

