Two prospective randomized trials (A2306 and A2307) have demonstrated that everolimus combined with steroids and low dose Neoral with (A2307) or without (A2306) basiliximab induction result in excellent 1 year outcomes (1). In 2002 we adopted an immunosuppressive regimen using Rapamune and reduced dose Neoral without steroids using induction therapy with Thymoglobulin. Since employing this regimen our acute rejection rate within the first year post-transplant has been between 7% and 10% for any given calendar year. However, many patients need to have their Rapamune discontinued due to drug related side effects or compliance difficulties related to the noon dosing (when most other medications are taken at 8 am and 4 pm). We feel strongly that use of an alternative drug to Rapamune in such cases is necessary. Use of Zortress in this setting would be ideal, however, no data currently exists concerning the use of Zortress with Neoral in a steroid free maintenance immunosuppression regimen following Thymoglobulin induction. Thus we propose this pilot study primarily to verify Zortress efficacy using our established immunosuppressive protocol. Secondarily we are interested in characterizing the Zortress drug related side effect profile to enable us in the future to exploit any favorable differences between Zortress and Rapamune.

2 Purpose and rationale

Our center's renal transplant immunosuppression protocol has consisted of Thymoglobulin and steroid induction for 5 doses only, with early initiation of Rapamune® (Sirolimus) and then Neoral for nearly a decade now. We do observe a significant amount of adverse events in our patient population, with many of these potentially related to the Sirolimus. The combination of "half-dose" cyclosporine (early C2 levels around 800 to 1000 ng/ml) allows us to minimize calcineurin inhibitor toxicity and its combination with the mTOR drug Sirolimus provides excellent protection against acute rejection in our renal transplant recipients. Our earlier experience with Everolimus and the recent publications describing renal recipients' outcomes with this drug, suggest to us that our patients may do better on Everolimus than Sirolimus (1,2). For our center, this pilot study would be very straightforward as the only difference in medication from our current well established protocol would be the randomization to either Rapamune®, our current standard of care, or Zortress®, the study drug.

3 Objectives

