3.3 Exploratory objectives

4 To explore the kidney and vascular endothelial function assessed by a panel of molecular markers over the observation period. Study design

Randomized, single center parallel-group, open-label study.

Pilot study with exploratory objectives.

Eligibility: All primary or retransplant recipients of deceased donor or living donor grafts with negative crossmatch who are felt to have good expectations for renal function recovery after surgery will be offered entry into the study.

Treatment scheme is as described above, with Solumedrol 500 mg IV in OR as induction, then 5 doses of Thymoglobulin starting morning of POD 1 at 1.25 mg/dose (rounded to nearest 25 mg) with rapid steroid taper over five doses. The mTOR inhibitor drug will be started on POD 0 and Neoral introduced as renal function recovers, usually starting on POD 2.

Measurement/Assessments: as described above, graft and patient survival per standard definitions, clinically indicated biopsies for determination of acute cellular or antibody mediated rejection, renal function as estimated from serum Cr based on MDRD, clinic visits for wound assessment, standard of care labs for renal function, bone marrow function (WBC and platelet count), liver function, lipid panel, donor specific antibody determination during any significant increase in serum Cr, drug levels routinely monitored for need of number of dose adjustments and compliance, Emergency Room and hospitalizations, as well as unscheduled clinic and other physician visits. For the pilot study, we would perform scheduled CMV, EBV and serum BK PCRs monthly for the first year, then quarterly or with any viral symptoms.

A subset of patients will have coded plasma samples sent to clinical research and development at the University of Colorado. These biomarker samples will be used to assess vascular endothelial dysfunction and inflammation markers as well as kidney dysfunction markers.

Plasma samples are collected and stored at The Ohio State University Wexner Medical Center tissue typing lab per standard of care.

5 Population

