6.5.1 Patient numbering

As this is an open-label study there will be no blinding and thus no need for patient identifying numbers as part of a blinding strategy.

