7.1 Table 7-1

Assessment schedule:

Visit number	1 Screening/ Baseline	2	3	4	5	6	7	8	9	10	11	12	13	14	15	16	17	18
Time of Visit		Day 0	Day 1	Day 2	Day 3	Day 4	Day 5 ¹	Day 6 ¹	Day 7 ¹	Wk 2	Mo 1	Mo 2	Mo 3	Mo 6	Mo 12	Mo 18	Mo 24	Mo 36
Inclusion/Exclusion criteria	X																	
Informed consent	X																	
Physical examination	X	X	X	X	X	X	X	X	X	X	X	X	X	X	X	X	X	X
Demographics	X																	
Medical History	X																	
Pregnancy Test ²	X																	
Vital signs	X	X	X	X	X	X	X	X	X	X	X	X	X	X	X	X	X	X
Hematology		X		X				X	X	X	X	X	X	X	X	X	X	X
Chemistry		X			X			X	X	X	X	X	X	X	X	X	X	X
Lipid panel	X									X	X	X	X	X	X	X	X	X
24 hour urine												X	X	X	X	X	X	X
Alloscreen	X															X		
Flow Crossmatch	X															X		
HGB A1C																X		X
Kidney Biopsy	X															X		
Adverse events		X	X	X	X	X	X	X	X	X	X	X	X	X	X	X	X	X
Cyclosporine level ³				X				X	X	X	X	X	X	X	X	X	X	X
Everolimus level ³					X			X	X	X	X	X	X	X	X	X	X	X
Optional sub study: Plasma for Biomarkers ⁴	X				X			X	X	X	X	X	X	X	X	X	X	X

Legend:

- 1: If still inpatient
- 2: Females capable of childbearing
- 3: Cyclosporine and Zortress levels are monitored twice weekly for 0-3 months post-transplant, every two weeks for 3-12 months post-transplant, and monthly greater than 1 year post-transplant.
- 4: Plasma for biomarkers will be assessed at the University of Colorado in a subset of patients using existing plasma samples.

Patients will be followed as per the standard of care at this transplant center (The Ohio State University Medical Center, Division of Transplantation). Additional study procedures include a protocol biopsy at month 12 and some additional laboratory work at screening/baseline and at months 6, 12, 24, and 36.

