10.1 Analysis of the primary objective(s)

10.1.1 Variable

The primary endpoint consists of non-death censored graft survival and biopsy proven acute rejection at 1 year post-transplant. These events will be directly measured and not calculated.

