10.1.2 Statistical hypothesis, model, and method of analysis

The primary endpoint will be a composite endpoint of graft survival (non-death censored) and biopsy proven acute rejection at 1 year.

Secondary endpoints at 6 months, 1, 2 and 3 years will include: graft survival and patient survival/death at 2 and 3 years, rate and grade of acute cellular rejection, rate of acute antibody mediated rejection, rate of new donor specific antibody formation, estimated CrCl by MDRD, lipid control as determined by requirement for anti-lipid medications and average levels with and without medications, ability to maintain initial immunosuppressive medications and reason for switch if required, wound complications as determined by need for wound packing, infection treatment with antibiotics, presence of hernia on exam and requirement for hernia repair, as well as presence of symptomatic lymphocele, and New Onset Diabetes After Transplant as determined by need for new oral or sustained Insulin medication.

Statistical analysis will be performed on SPSS or STATA software with dichotomous variables evaluated by Chi-Squared analysis, continuous variables by Student's T-Test, non-parametric outcomes will be assessed by Wilcoxon rank sum test (Mann-Whitney U test). Kaplan-Meier survival curves with log rank tests will be used to determine a difference in graft and patient survival over time.

Safety data will include patient and graft survival, biopsy proven acute rejection, and hospital admissions.

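### Section 6.4 rules out all blinding and nothing provides for arm-masked reading of the biopsies behind the rejection component of the primary endpoint; this is a cheap improvement

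*Combined protocol and SAP*

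**What the plan says.** Section 6.4 (Treatment blinding) is one sentence: "This is an open-label study and thus there will be no blinding". Section 6.5.1 (Patient numbering) repeats that "there will be no blinding and thus no need for patient identifying numbers as part of a blinding strategy". Neither makes an exception for people who assess outcomes.

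Section 10.1.2 defines the primary endpoint: "The primary endpoint will be a composite endpoint of graft survival (non-death censored) and biopsy proven acute rejection at 1 year". Sections 3.1 and 10.1.1 agree.

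Biopsies enter the plan in two ways. The study design section lists "clinically indicated biopsies for determination of acute cellular or antibody mediated rejection". The text under Table 7-1 adds a scheduled one: "Additional study procedures include a protocol biopsy at month 12". Section 3.2 makes the grade of rejection episodes and the 12-month histology secondary outcomes.

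No section says who reads the biopsies, what the reader is told, or which grading criteria apply. None describes adjudication or masked reading.

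**The concern.** Section 6.4 treats the absence of blinding as a consequence of open-label treatment. That follows for patients and treating clinicians. It does not follow for the person who grades a biopsy, who can work without knowing which mTOR inhibitor the patient takes.

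Grading rejection involves judgement in borderline cases. The plan also states an expectation: section 2 suggests that patients may do better on everolimus than on sirolimus, and section 10.5 expects non-inferiority of Zortress. A judgement made with the arm in view is most exposed to bias when one result is expected.

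The trial is small and few rejection events are likely, so each reading carries weight in the primary comparison. Section 6.5.6 also makes a statistically significant difference in primary outcome one of the conditions for considering early termination.

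**Working it through.** The plan gives no event count, alpha, margin or power for this endpoint, so there is no figure of its own to reproduce.

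**Inputs**
- Sample size 60 (section 6.2), allocated 2:1 (sections 5 and 6.2): 60 × 2/3 = 40 on Zortress and 60 × 1/3 = 20 on Rapamune.
- First-year acute rejection rate 7% to 10% (section 1, Background). This is the centre's experience with the Rapamune regimen; applying it to both arms is an assumption.
- Chi-squared test for dichotomous outcomes (section 10.1.2). No continuity correction and a two-sided 0.05 level are assumed, because the plan states neither.

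**Expected rejection events** (patients × rate)
- All patients: 60 × 0.07 = 4.2 to 60 × 0.10 = 6.0.
- Zortress: 40 × 0.07 = 2.8 to 40 × 0.10 = 4.0.
- Rapamune: 20 × 0.07 = 1.4 to 20 × 0.10 = 2.0.

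**Weight of one reading**
- Zortress: 1/40 = 2.5 percentage points.
- Rapamune: 1/20 = 5 percentage points.

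**From the expected position at 10%**

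Differences are Zortress minus Rapamune.

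| Zortress | Rapamune | Difference (points) | Chi-squared p |
|---|---|---|---|
| 4/40 | 2/20 | 0 (95% CI -16.1 to +16.1) | 1.00 |
| 3/40 | 2/20 | -2.5 | 0.74 |
| 4/40 | 3/20 | -5.0 | 0.57 |
| 3/40 | 3/20 | -7.5 | 0.36 |
| 4/40 | 4/20 | -10.0 | 0.28 |

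One or two changed readings move the estimate but come nowhere near 0.05.

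**From a position already near the threshold, also with six events**

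| Zortress | Rapamune | Difference (points) | Chi-squared p |
|---|---|---|---|
| 2/40 | 4/20 | -15.0 | 0.068 |
| 1/40 | 4/20 | -17.5 | 0.021 |
| 2/40 | 5/20 | -20.0 | 0.023 |

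Here a single reading crosses 0.05. Fisher's exact test crosses too for the first change (0.089 to 0.038). This start was chosen because it lies close to the threshold.

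**Rejection's share of primary events**

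Let r be the rejection rate and g the 1-year rate of graft loss or death without prior rejection. The share is r/(r + g). The documents give no g, so it is varied as an assumption:
- g = 2%: 7/9 = 78% to 10/12 = 83%.
- g = 5%: 7/12 = 58% to 10/15 = 67%.
- g = 12%: 7/19 = 37% to 10/22 = 45%.

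Rejection supplies more than half of the events only if g is below r.

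**The case against.** The strongest reply is that this is a declared pilot. Section 3.2 calls all objectives exploratory, section 10.3 disclaims power, and shifts of 2.5 or 5 points are small beside a confidence interval of about ±16 points. That is why the point is an improvement and not a serious defect. It does not remove the point: masking addresses bias and not power, and section 3.1 still sets equivalency as the primary objective.

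A second reply also stands. Masking the reader leaves the larger problem in place, because unmasked clinicians decide who is biopsied for cause.

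Third, the documents separate the two kinds of biopsy. Rejection is tied to clinically indicated biopsies, whereas the month-12 biopsy is listed as a secondary outcome on graft injury. They do not say whether rejection found at month 12 counts toward the primary endpoint, so masked reading of that biopsy may protect only secondary results.

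Several stronger readings are tempting and fail:
- A reader might infer that biopsies are graded with the arm known. Section 6.4 is headed treatment blinding, and no section says what the biopsy reader knows.
- A reader might infer that rejection supplies most primary events. That depends on a rate of graft loss or death that the documents omit; over the range assumed above, the share runs from 37% to 83%.
- A reader might infer that two biased readings suffice for significance, since 0/40 v 2/20 gives chi-squared p = 0.042. That uses two events where 4 to 6 are expected. Fisher's exact p is 0.11, and the expected event counts are only 1.33 and 0.67, so the small p-value reflects the choice of test.

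**Conclusion.** The point holds as a cheap improvement. The plan excludes blinding without exempting outcome readers and does not provide for arm-masked reading of a judgement-based component of its primary endpoint. Nothing about open-label treatment requires that.

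The effect is on the estimate: 2.5 or 5 points per changed reading, with about 4 to 6 rejection events expected. It changes the significance of the result only when that is already marginal. The sizes rest on the centre's historical rate applying to both arms and, for the p-values, on an uncorrected two-sided test at 0.05.

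The documents support neither a claim that readings are in fact biased nor a claim that the reader is told the arm.

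**What to change.** Amend section 6.4 to say that treatment is open-label, but that for-cause and month-12 biopsies are graded with the arm withheld by whoever already reads them. The biopsy request should say 'mTOR inhibitor' and not the drug name, and the grade should be recorded before the arm is looked up. Record the clinical indication for every for-cause biopsy, so that any difference between arms in the threshold for biopsy can be examined. State whether rejection found on the month-12 biopsy counts toward the primary endpoint.

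The cost should be small: wording on the request and one recorded field, with no added biopsy. This assumes that a routine pathologist reads the slides, so that no extra reader is needed; the documents name neither the reader nor a cost. Sample size, alpha and power do not change.

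Two limits should be stated in the protocol. Masking is incomplete if the reader opens the chart. The decision to biopsy for cause stays unmasked, so ascertainment bias remains.
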